# 8.1.1 Screening Period

The Screening Period is defined as the three-week period prior to Week 0 (IMP administration).

Before the initiation of study-specific screening assessments, the subject must be given a complete explanation of the purpose of the study and evaluations that will be made as part of the study. Subsequently, the subject must sign and receive a copy of an Informed Consent Form that was approved by the Institutional Review Board (IRB)/Independent Ethics Committee (IEC). Once informed consent has been obtained, the eligibility of the subject to participate in this study will be determined by the Investigator on the basis of the inclusion and exclusion criteria in Section 7.4. Screening Period assessments will also be performed to determine eligibility. Only eligible subjects will be randomized to receive IMP at Week 0.

Following a discussion of participation in the clinical study and signed informed consent obtained, the following procedures will be performed to determine the subject's eligibility for this study (Table 8–1) during the Screening Period (Week -3 to Week 0):

- Informed Consent
- Interview to collect subject medical history, including but not limited to, disease history (including asthma history, number of asthma exacerbations in the previous year, hypersensitivity to aspirin or other NSAIDs), surgical history (including the number and dates of previous nasal polypectomies), recently discontinued and concomitant medications (include all background therapy for AERD).
- Demographic data
- Administer SNOT-22.
- Perform spirometry to ensure the subject has stable asthma (FEV1 ≥ 60% of predicted normal and has not experienced any exacerbation requiring treatment with ≥ 1 systemic (oral or parenteral) steroid bursts for worsening asthma and/or hospitalization or an emergency/urgent medical care visit for worsening asthma in the previous three months or are on a dose of inhaled corticosteroids > 1000 µg fluticasone or equivalent daily).
- Obtain fasting blood samples for screening clinical laboratory determinations:
  - Hematology: To include hemoglobin, hematocrit, platelet count, total white blood cell count with five-part differential count, and total red blood cell count.

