3.2 Secondary Objectives

- Evaluate the effect of ifetroban on asthma symptoms by forced expiratory volume 1 (FEV1) compared to baseline.
- Assess nasal symptoms and QoL using the peak Nasal Inspiratory Flow Rate (PNIFR), University of Pennsylvania Smell Identification Test (UPSIT), fractional exhaled nitric oxide (FeNO), Asthma Control Questionnaire (ACQ) - 7 and Total Nasal Symptom Score (TNSS)
- Determine whether ifetroban reduces the frequency and severity of asthma exacerbations and chronic sinusitis as well as the frequency of rescue medication and antibiotic use.
- Evaluate the pharmacodynamic effects of TPr blockade on eicosanoids and eosinophil count.

[figure not shown]

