4.3 Randomization and Blinding

Subjects who meet all the inclusion and no exclusion criteria during the Screening/Baseline Period will be randomized using a 1:1 randomization ratio to receive either ifetroban 200 mg once daily or matching placebo. A central randomization will be utilized. Approximately 76 subjects shall be randomized to ensure at least 38 subjects per group will be analyzed for efficacy

The study will be double blind with respect to the treatment assignment. To maintain the study blind, the appearance of packaging and capsules will be identical in both study arms. Site and CPI clinical staff will be blinded to the treatment assignment until the completion of the study. Individual treatment assignment will remain blinded throughout the study. In the event a treatment assignment needs to be unblinded for safety reasons, the site principal investigator will notify the study project manager, who will consult with the medical monitor. The medical monitor will review the circumstances and grant approval as indicated. Any intentional or unintentional breaking of the blind will be reported to the Sponsor immediately and fully documented in the subject's case report form.

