4.5 Sample Size Determination

Thirty-eight subjects per group will provide 90% power for the comparison of ifetroban and placebo with respect to the change from baseline in SNOT-22 scores at Week 8 (two-sided, level 0.05), assuming a common standard deviation of 16 and a true difference is 12.

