 - CFB ACQ = post-treatment measurement – baseline
 - Any improvement in ACQ-7 (Yes or No): If CFB ACQ<0, then improvement =’Yes’; otherwise improvement = ‘No’
- Total Nasal Symptom Score (TNSS) AM and PM measurements
 - TNSS Daily Score = sum of the 4 symptom scores (congestion, runny_nose, nasal_itching, sneezing) for both AM and PM, separately. (listed only)
 - TNSS Visit Score: The daily score for AM and PM are averaged over time between the visits separately. Baseline Visit Score for AM and PM is obtained by averaging over the screening period and the day of the baseline visit. Week 4 Visit Score is obtained by averaging over the day after the baseline visit to the day of the Week 4 visit. Week 8 Visit Score is obtained by averaging over the day after Week 4 visit to the day of the Week 8 visit. Week 10 Visit Score is obtained by averaging over the day after Week 8 visit to the day of Week 10 visit.
 - CFB TNSS Visit Score = post-treatment measurement – baseline
- Frequency and Severity of Asthma Exacerbations (Respiratory Reaction Questionnaire)
 - Subject Frequency =count the number of reports since the previous visit for each visit
 - CFB Frequency = post-treatment measurement – baseline
 - Max Severity= define the maximum severity for each subject (none, mild, moderate, or severe) over the period since the previous visit.
 - Inhaler or rescue med (number of reports) count= count the number of reports where resp_rxn_inhaler >0 OR resp_rxn_add_tx_yn=Yes
 - CFB Inhaler or rescue= post-treatment measurement – baseline

- Frequency and Severity of Chronic Sinusitis (Sinus Infection Questionnaire)
 - Antibiotic use Frequency (number of reports) count= count the number of reports over the period since the previous visit where sinus_inf_antibio=yes
 - CFB Antibiotic use= post-treatment measurement – baseline

Pharmacodynamic Variables and biomarkers

- Plasma - Data from third party vendor
 - ScD10L (pg/mL)
 - Sp_selection (ng/mL)
- Biomarkers - Data from third party vendor.
 - Urine LTE4 (ng/mg Creatinine)
 - Urine PGD-M (ng/mg Creatinine)
 - Urine TX-M (ng/mg Creatinine)
 - Plasma F2 Isoprostanes (ng/mL)
 - Serum LTB4 (ng/mL)
 - SAM-Eicosanoids PGD2 (ng/mL)
 - SAM-Eicosanoids PXA2 (ng/mL)
 - SAM-Eicosanoids F2 Isoprostanes (ng/mL)

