7 EFFICACY ANALYSES

All hypothesis tests will be performed at the 0.05 level. Analyses of the primary efficacy variables will be performed using both the ITT and PP Populations; analyses of secondary efficacy variables will be performed using the ITT population only. Summary statistics will be presented for all analyses of efficacy variables.

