7.2 Secondary Efficacy Analyses

The analyses performed for the secondary efficacy variables will be combinations of summary statistics and ANCOVAs, using the normal approximation to the binomial (see Appendix A for details.) as appropriate, at specified visits presented in the table below.

The ANCOVA will include the corresponding value at Baseline as the only covariate with treatment. The LS means, standard error and p-values will be presented with corresponding the summary statistics.

Categorical variables will be analyzed using the normal approximation to the binomial distribution, assuming unequal variances. The p-value will be presented along with summary statistics.

The chart below outlines the analyses to be performed on each variable. It identifies the weeks in which the analysis will be performed for the variable of interest, the population, and the type of imputation.

Variable Name	Value Type	Pop	Weeks for Analysis			Imputation (2)
			Summary	ANCOVA	Binomial (1)	
SNOT-22	Score PCFB	ITT	0,4,8,10			LOCF
	Improvement(y/n)	ITT	0,4,8,10		4,8,10	NRI
SNOT-22 Subscale	Nasal Related	ITT	0,4,8,10			LOCF
	Ear and Facial	ITT	0,4,8,10			LOCF
	Quality of Life	ITT	0,4,8,10			LOCF
	Psychological	ITT	0,4,8,10			LOCF
	CFB Nasal Related	ITT	0,4,8,10			LOCF
	CFB Ear and Facial	ITT	0,4,8,10	4,8,10		LOCF
	CFB Quality of Life	ITT	0,4,8,10	4,8,10		LOCF
	CFB Psychological	ITT	0,4,8,10	4,8,10		LOCF
	22 Questions	ITT	0,4,8,10			LOCF
FEV1	Value	ITT	0,4,8,10			LOCF
	CFB	ITT	0,4,8,10	4,8,10		LOCF
PNIFR	Value	ITT	0,4,8,10			LOCF
	CFB	ITT	0,4,8,10	4,8,10		LOCF
UPSIT	Value	ITT	0,4,8,10			LOCF
	CFB	ITT	0,4,8,10	4,8,10		LOCF
FeNO	Value	ITT	0,4,8,10			LOCF
	CFB	ITT	0,4,8,10	4,8,10		LOCF
ACQ	Value	ITT	0,4,8,10			LOCF
	CFB	ITT	0,4,8,10	4,8,10		LOCF
	Improvement (y/n)	ITT	0,4,8,10		4,8,10	NRI

(1) Normal approximation to the Binomial
 (2) Imputation analysis outlined in Section 5.1. NRI=Non responder imputation, LOCF=Last observation carried forward

Variable Name	Value Type	Pop	Analysis			
			Summary	ANCOVA	Binomial (1)	Imputation (2)
TNSS AM/PM	Visit Score	ITT	4,8,10			LOCF
	CFB Visit score	ITT	4,8,10	4,8,10		LOCF
Asthma	Reports	ITT	0,4,8,10			LOCF
	CFB Reports	ITT	0,4,8,10	4,8,10		LOCF
	Max Severity	ITT	0,4,8,10			LOCF
	Rescue report	ITT	0,4,8,10			LOCF
	CFB rescue report	ITT	0,4,8,10	4,8,10		LOCF
Sinusitis	Reports	ITT	0,4,8,10			LOCF
	CFB Reports	ITT	0,4,8,10	4,8,10		LOCF
	Max Severity	ITT	0,4,8,10			LOCF
	Antibiotic report	ITT	0,4,8,10	4,8,10		LOCF

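### Asthma exacerbation reports and sinus-infection antibiotic reports are tested only in separate between-visit windows, so no test or estimate covers the eight weeks on drug

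*SAP*

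**What the plan says.** The secondary objective in SAP 3.2 is to "Determine whether ifetroban reduces the frequency and severity of asthma exacerbations and chronic sinusitis", along with the frequency of rescue medication and antibiotic use.

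SAP 4.6 defines the exacerbation variable as "Subject Frequency =count the number of reports since the previous visit for each visit". Maximum asthma severity and the count of sinus-infection reports with antibiotic use are also taken over the period since the previous visit. The inhaler-or-rescue count has no stated window. The sinusitis Reports variable has no definition in 4.6, although 7.2 tests its change from baseline.

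The table in SAP 7.2 gives ANCOVAs at Weeks 4, 8 and 10 for four of these rows: asthma CFB Reports, CFB rescue report, sinusitis CFB Reports and sinusitis Antibiotic report. On the model it says: "The ANCOVA will include the corresponding value at Baseline as the only covariate with treatment". With visits at Weeks 0, 4, 8 and 10, the windows are Weeks 0–4, Weeks 4–8 and the post-treatment Weeks 8–10.

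Neither document defines a cumulative on-treatment count, an event rate or a time-to-first-event analysis. SAP 5.4 makes no multiplicity adjustment. Protocol 11.6.3.2 plans its change-from-baseline analyses at Weeks 4 and 8 only; the Week 10 test appears in the SAP alone.

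**The concern.** A between-visit layout suits SNOT-22, which measures a state at each visit. It does not suit event counts. The result labelled Week 8 discards every event in Weeks 0–4, and the Week 10 result contains only time off drug. A reader who asks whether ifetroban reduced exacerbations during treatment gets up to three p-values and no estimate for the treatment period.

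Two things are at stake. If one window is read as the answer, half of the on-drug observation time is unused and power falls. If any favourable window may be claimed, the false-positive risk rises above the nominal level. The plan has no rule for the case where the two on-drug windows disagree.

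**Working it through.** **Inputs from the documents.** Test level: "All hypothesis tests will be performed at the 0.05 level". Sidedness and the SNOT-22 planning values: "two-sided, level 0.05), assuming a common standard deviation of 16 and a true difference is 12". Size: "Thirty-eight subjects per group will provide 90% power for the comparison of ifetroban and placebo". Allocation: subjects "will be randomized using a 1:1 randomization ratio to receive either ifetroban 200 mg once daily or matching placebo". On-drug time is 8 weeks, in windows of 4 + 4, and off-drug time is 2 weeks. The baseline count covers up to 2 weeks (SAP 4.1) or up to 3 weeks (Protocol 7.1).

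**Assumed, because the documents give none.** Placebo rate 0.2 to 4 reports per 8 weeks; rate ratio (RR) 0.5 to 0.7; between-subject gamma variance k from 0 (Poisson) to 2; complete follow-up.

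**Step 1: the plan's own power figure.** n = 2(1.960 + 1.282)² × 16²/12² = 37.4, so 38 per arm. Power = Φ(12/(16√(2/38)) − 1.960) = 90.5% (89.7% with the t distribution). The stated 90% reproduces. It concerns SNOT-22 only; no power is given for the event endpoints.

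**Step 2: halving the information.** For Poisson counts with a constant effect, a 4-week window carries half the information of 8 weeks:

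power(4 weeks) = Φ((1.960 + z)/√2 − 1.960), where z = Φ⁻¹(power at 8 weeks).

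For 80% at 8 weeks: (1.960 + 0.842)/1.414 − 1.960 = 0.021, so 51%. Likewise 50% falls to 28%, 70% to 42%, 90% to 63% and 95% to 72%. The relative losses for 50, 70, 80, 90 and 95% are 43, 40, 37, 30 and 24%.

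**Step 3: simulating the SAP's ANCOVA** (count on baseline count and treatment, 38 per arm, 2-week baseline, 8,000 trials per setting, constant effect). Because baseline is a covariate, analysing the count or its change gives the same treatment test.

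| Placebo reports per 8 weeks | RR | k | Weeks 0–8 count | Weeks 0–4 / 4–8 window | Relative loss |
|---|---|---|---|---|---|
| 0.2 | 0.7 | 2 | 7.0% | 5.2% / 5.7% | 22% |
| 0.5 | 0.5 | 0 | 42.6% | 22.9% / 23.6% | 46% |
| 1 | 0.5 | 0 | 69.8% | 41.9% / 41.4% | 40% |
| 1 | 0.6 | 1 | 30.0% | 19.7% / 20.4% | 33% |
| 2 | 0.6 | 1 | 45.8% | 32.4% / 32.9% | 29% |
| 4 | 0.5 | 1 | 86.6% | 73.7% / 73.4% | 15% |
| 4 | 0.5 | 0 | 99.8% | 94.3% / 94.5% | 5.5% |
| 4 | 0.7 | 0 | 79.7% | 50.7% / 50.2% | 37% |

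Over the whole grid the relative loss is 22–46% at up to 2 reports per 8 weeks. At 4 per 8 weeks it is 5–37%, or 12–27% once k is 0.5 to 2. The largest absolute loss is about 30 percentage points.

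**Step 4: using both on-drug windows.** At 1 report per 8 weeks, RR 0.5, k = 0, a win in either window has 65.8% power, against 69.8% for the pooled count; requiring both gives 17.5%. With no effect, two independent tests give 1 − 0.95² = 9.75% false positives; the simulation gave 10.0% (k = 0) and 8.8% (k = 1). The Week 10 test rejects about 5% of the time at most if the effect stops with dosing (an assumption).

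**Step 5: onset.** RR 0.5 in Weeks 4–8, k 0.5 to 1, 3-week baseline. Each cell shows the Weeks 4–8 window against the Weeks 0–8 count.

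| RR in Weeks 0–4 | 0.5 per 8 weeks | 1 per 8 weeks | 2 per 8 weeks |
|---|---|---|---|
| 0.5 (constant) | about 20% v 33–36% | 31–35% v 49–57% | 53–59% v 72–80% |
| 0.75 (gradual) | 19–21% v 18–19% | 31–36% v 28–35% | 50–59% v 43–52% |
| 1 (no early effect) | 19–21% v 10–11% | 31–38% v 13–16% | 53–59% v 21–24% |

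**Step 6: window or model?** Under a constant effect, ANCOVA on the Weeks 0–8 total has power 30–35%, 49–57% and 72–81% at the three rates. A quasi-Poisson model on the same total has 30–34%, 49–57% and 73–81%. The gain comes from not splitting the events, not from the model.

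**The case against.** The strongest counter-argument is onset. Protocol 5.1 distinguishes short-term receptor blockade from the longer-term suppression of eosinophilic inflammation, so a delayed effect cannot be dismissed. Step 5 shows that the Weeks 4–8 window then matches or beats the pooled count, and beats it clearly if nothing happens in Weeks 0–4. This stands. It is a reason to keep the windows as supportive analyses and to state any power loss as conditional. It does not supply the missing estimate for the treatment period.

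Second, the SAP tests Weeks 0–4 as well as Weeks 4–8, so a real reduction has two chances to show. That is true, but without a named main window or an adjustment the second chance costs a false-positive risk of about 9–10%.

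Third, these are secondary and exploratory endpoints without a power claim in a proof-of-concept trial, and the objective does not itself mention eight weeks. This limits the weight of the point. However, eight weeks is the randomized treatment period, and it is the natural period for a frequency claim.

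A reader might also infer three things that the documents do not support:

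- **That the stable-asthma rule drives the baseline count to zero.** The rule bars steroid bursts, hospitalizations and emergency visits. The endpoint counts questionnaire reports that may be mild.
- **That adjusting for the previous-year history would certainly add power.** Protocol 8.1.1 collects the "number of asthma exacerbations in the previous year" at interview, but nothing shows that it measures the same event as the questionnaire.
- **That the sinusitis Reports count is explicitly windowed.** Its definition is missing; only antibiotic reports have a stated between-visit period.

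**Conclusion.** The point holds as a gap in the analysis plan. Exacerbation reports and sinus-infection antibiotic reports are analysed only by between-visit window, and no test or estimate covers the time on drug. No window has priority, so the frequency objective has no single answer. That conclusion follows from the text and needs no assumption.

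The size is conditional. With a constant effect from the first dose, complete follow-up and 38 per arm, one four-week test loses about 22–46% of the power of a Weeks 0–8 count at up to 2 events per 8 weeks, and about 5–37% at 4. It is tempting to say flatly that a third to nearly half of the power is lost. The documents do not support that: they give no event rate, dispersion or onset time, the loss shrinks when events are frequent or vary strongly between subjects, and its direction can reverse with late onset.

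Only secondary endpoints are affected. This should be corrected before unblinding, but it does not threaten the primary conclusion.

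**What to change.** **SAP 4.6.** Define the sinusitis Reports count and give the rescue count a window. Add one on-treatment count per subject, from first dose to Week 8 or exit, for exacerbations and for sinus infections.

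**SAP 7.2.** Name the between-arm comparison of each on-treatment count as the main frequency analysis. Report a rate ratio with 95% CI from a negative-binomial or quasi-Poisson model with log days observed as offset. The reason for this model is interpretability and unequal follow-up, not extra power. Because it uses the days actually observed, it does not need a count carried forward from one window to another, or a baseline count over 2 or 3 weeks subtracted from a 4-week count.

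Keep the Weeks 0–4 and 4–8 counts as supportive, to show onset, and Weeks 8–10 as off-treatment description without a test. The previous-year exacerbation count may serve as an optional sensitivity covariate for the asthma endpoint. Record the change in SAP Section 9.

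**Cost.** SAP wording and one model per endpoint, with no new data or visits. SAP Section 1 already allows revision before any unblinded analysis. The statistical price is that a late-starting effect is diluted in the pooled count, which is why the on-drug windows stay in the plan.

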4.7 ANALYSIS POPULATIONS

Safety Population All subjects who received at least one dose of study medication will be included in the Safety Population.

Intent-to-Treat Population The Intent-To-Treat (ITT) Population will consist of all treated subjects with at least one post-baseline assessment of SNOT-22.

Per Protocol Population The Per Protocol (PP) Population will consist of all subjects in the ITT population with no major protocol violations, including violation of inclusion or exclusion criteria or insufficient dosing. Inclusion of subjects in the PP Population will be determined prior to unblinding.

5. GENERAL STATISTICAL CONSIDERATIONS

The following text provides general description of the statistical methodology for the assessment of efficacy, safety, and tolerability of 200 mg/day of oral ifetroban in this double-blind placebo-controlled study in subjects with symptomatic AERD.

Appropriate summary statistics will be provided for categorical data (n, %) and for continuous data (n, mean, standard deviation, minimum, median, maximum). All recorded data will be listed by subject and by visit unless otherwise specified.

5.1 Handling of Dropouts or Missing Data

Missing efficacy data which are not retrievable through queries will be imputed.

NRI

Binary response efficacy variables will be imputed by treating the missing data as a failure, ie, non-responder imputation (NRI). A response variable that is calculated from a continuous variable will only be imputed using NRI, not from the imputed continuous variable.

LOCF

Missing data for continuous efficacy variables with at least one post-baseline measurement will be imputed using Last Observation Carried Forward (LOCF). Any calculated continuous variable will be imputed after its creation.

If the baseline value is missing for any variable, then the last screening value will be used.

MI

Multiple imputation (MI) will be provided as a sensitivity analysis for the primary efficacy variable (SNOT-22 Score CFB) only. Six imputations will be calculated from PROC MI. Week 8 will be imputed using week 0 and week 4 by treatment by treatment. The analysis will be performed on the 6 imputed sets which will provide 6 estimates of LS means from separate analyses of ANCOVAs (see Section 7.1).

```
proc mi data=thedata out=outds n impute=6 seed=310
min=(-110 -110 -110 -110 -110 -110)
max=(110 110 110 110 110 110)
round=(1 1 1 1 1 1)
minmaxiter=100
noprint;
by trt;
var SNOT22BASE SNOT22CFB4 SNOT22CFB8;
run;
```

where SNOT22BASE is the baseline SNOT22 score and, SNOT22CFB4 and SNOT22CFB8 are the SNOT-22 Score values at Weeks 4 and 8, respectively.

The seed specified above will be used for development, but may be changed prior to unblinding; any such change will be documented. If convergence is not achieved with minmaxiter=100, then increase the number of iterations to 500. The properties of this approach, including convergence and collinearity, will be assessed prior to unblinding and may be adjusted to improve the operating characteristics.

After calculating the LS means of the two treatments and the estimated treatment difference and associated standard error from the ANCOVA, the 6 estimates can be placed in PROC MI analyze.

Code to obtain a single estimate of the treatment LS means and standard error.

```
proc mianalyze=thedata ; **Data output from proc mixed;  
by trt;  
modeleffects estimate; ***estimate of lsmeans for 6 sets;  
stderr stderr; *** estimate of standard error for 6 sets;  
run;
```

Code to obtain a single estimate p-value for the treatment difference.

```
proc mianalyze=thedata ; **Data output from proc mixed with /diff option  
modeleffects diffestimate; ***estimate of the treatment difference for 6 sets;  
stderr diffstderr; *** estimate of treatment difference standard error for 6 sets;  
run;
```

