#### 8 STUDY VISITS AND PROCEDURES

# 8.1 Overview – Schedule of Time and Events

This 13-Week study will consist of a three-week Screening Period (Week -3 to Week 0), an 8-week Treatment Period (Week 0 to Week 8) and a two-week Post-treatment Period (Week 8 to Week 10). The study visits occur on the planned dates relative to the first dose of IMP as scheduled. The visit schedule should be adhered to within the  $\pm$  5 day visit window.

If a subject is prematurely discontinued from treatment, all assessments planned at the End of Treatment visit should be performed. Prior to all screening assessments, after discussion of participation in the study, the written consent form must be signed and dated. Although the screening assessments for this study are grouped under the heading of a single visit in this protocol, it is possible for them to be performed over more than one site visit if necessary, as long as the three-week screening period relative to the first dose of IMP is respected. Subjects that fail screening for exclusion criteria, for example concomitant medications, acute illness (upper respiratory tract infection), required drug-specific discontinuation periods or laboratory tests, may be rescreened for study eligibility one additional time.

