#### If the subject meets all inclusion and does not meet any exclusion criteria:

- Subject will be randomized
- PNIFR and FeNO will be recorded
- Perform serum/urine pregnancy test (for women of childbearing potential). Confirm subject is protected by one of the following acceptable forms of effective contraception during the study:
  - Established use of oral, injected or implanted hormonal contraceptive
  - "Double barrier" methods (i.e., Double Intrauterine device with copper or intrauterine system with progestogen and barrier contraceptive [condom, diaphragm or cervical/vault caps] used with spermicide [foam, gel, film, cream or suppository])
  - Female sterilization (e.g., tubal occlusion, hysterectomy or bilateral salpingectomy)
  - Male sterilization with post-vasectomy documentation of the absence of sperm in the ejaculate; for female subjects enrolled in the study, the vasectomized male partner should be the sole partner for that subject
- Perform blood sampling (prior to administration of IMP) for clinical laboratories: hematology, chemistry, PT, and INR.

Note: Clinical laboratory testing at Week 0 Visit is limited to biomarkers in serum and plasma if screening labs were performed within three weeks of starting IMP treatment.

- Collect urine and blood samples for eicosanoid metabolites.
- Collect nasoabsorptive matrix for eicosanoid measurements.

- Conduct a smell test (UPSIT)
- Collect data from subject diary and remind subject to record daily medication usage including IMP, exacerbations, rescue medication or antibiotic usage, if applicable, twice daily TNSS (AM and PM) and to bring their diary to the next visit
- Pre-IMP Dietary Assessment
- Dispense IMP and administer IMP
- Commence AE reporting
- Schedule appointment for next visit

Treatment Period (Week 0 to Week 8): Subjects will take ifetroban or placebo daily for eight weeks. There will be a telephone encounter one week into this Treatment Period to ensure safety and confirm that baseline asthma symptoms have not worsened.

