#### **Week 4 Treatment Visit**

After four weeks of treatment, subjects will return to the site for Week 4 Treatment Visit.

- Record all medication use with start date and dose and check for prohibited medications.
- Inquire about AEs/Serious Adverse Events (SAEs) and IMP tolerability
- Perform a limited physical exam with vital signs (blood pressure, heart rate, respiration rate, body temperature, weight)
- Administer TNSS, ACQ-7, and SNOT-22
- Obtain spirometry, PNIFR and FeNO
- Perform serum/urine pregnancy test (for women of childbearing potential) Confirm subject is protected by one of the following acceptable forms of effective contraception during the study:
  - Established use of oral, injected or implanted hormonal contraceptive
  - "Double barrier" methods (i.e., Double Intrauterine device with copper or intrauterine system with progestogen and barrier contraceptive [condom, diaphragm or cervical/vault caps] used with spermicide [foam, gel, film, cream or suppository])

- Female sterilization (e.g., tubal occlusion, hysterectomy or bilateral salpingectomy)
- Male sterilization with post-vasectomy documentation of the absence of sperm in the ejaculate; for female subjects enrolled in the study, the vasectomized male partner should be the sole partner for that subject
- Collect urine and blood samples for eicosanoid metabolites.
- Collect nasoabsorptive matrix for eicosanoid measurements.
- Conduct a smell test (UPSIT)
- Review subject diary for IMP compliance, content and completeness; collect data from subject diary and remind subject to continue recording daily medication usage including IMP, time of meals and doses, exacerbations, rescue medication or antibiotic usage (if applicable), twice daily TNSS (AM and PM) and to bring their diary to the next visit
- Dispense IMP and administer IMP
- Schedule appointment for next visit

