4.6 Study Variables

Efficacy Variables

- SNOT-22 score (Sino-Nasal Outcome Test)
 - Total Score = Sum of the values collected in the 22 questions collected in the database.
 - CFB (change from baseline) total score = post-treatment measurement - baseline
 - PCFB (percent change from baseline) = (post-treatment measurement – baseline)/baseline
 - Improvement in SNOT-22 (Yes or No): if CFB (SNOT-22) <0, then improvement = 'Yes'; otherwise improvement = 'No'
 - Nasal Related Subscale = sum of the following questions to calculate the subscale: "need to blow nose", "sneezing", "runny nose", "nasal obstruction", "loss of smell/taste", and "post-nasal drip",
 - Ear and Facial Related Subscale = sum of the following questions to calculate the subscale: "ear fullness", "dizziness", "ear pain", "facial pain and pressure"
 - Quality of Life Related Subscale = sum of the following questions to calculate the subscale: "difficulty falling asleep", "wake up at night", "wake up tired", "fatigue", "reduced productivity", "reduced concentration"
 - Psychologically Related Subscale = sum of the following questions to calculate the subscale: "frustrated/restless/irritable", "sad", "embarrassed"
 - CFB Nasal Related Subscale = post-treatment measurement visit - baseline
 - CFB Ear and Facial Related Subscale = post-treatment measurement visit – baseline
 - CFB Quality of Life Related Subscale = post-treatment measurement visit - baseline
 - CFB Psychologically Related Subscale = post-treatment measurement visit - baseline
- Forced Expiratory Volume 1 (FEV1)
 - FEV1 Value = Collected on the CRF. Measured as the "best effort" of the 3 collected measurements at each time point where "best effort"= Max (fev1_1, fev1_2, fev1_3)
 - CFB FEV1 = post-treatment measurement – baseline

- Peak Nasal Inspiratory Flow Rate (PNIFR)
 - PNIFR value= Measured as the “best effort” of the 3 collected measurements at each time point where “best effort”= Max(pnfr1, pnfr2, pnfr3)
 - CFB PNIFR = post-treatment measurement - baseline
- University of Pennsylvania Smell Identification Test (UPSIT)
 - UPSIT value - Calculated by staff. Found in the database.
 - CFB UPSIT= post-treatment measurement – baseline
- Fractional exhaled Nitric Oxide (FeNO)
 - FeNO value – Collected on the CRF.
 - CFB FeNO = post-treatment measurement - baseline
- Asthma Control Questionnaire (ACQ) – average of non-missing values
 - ACQ score. Calculated in database (ACQ_Score)

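### Non-responder imputation does not reach treated subjects with no post-baseline SNOT-22, because the ITT set used for the responder analyses leaves them out

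*SAP*

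**What the plan says.** **Imputation rule.** SAP 5.1 says "Binary response efficacy variables will be imputed by treating the missing data as a failure" (non-responder imputation, NRI). It adds: "A response variable that is calculated from a continuous variable will only be imputed using NRI, not from the imputed continuous variable". Neither sentence requires a post-baseline value. The LOCF rule that follows in the same section does require one, for continuous variables.

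**Response.** SAP 4.6 defines SNOT-22 improvement as any fall from baseline: "if CFB (SNOT-22) <0, then improvement = 'Yes'; otherwise improvement = 'No". ACQ-7 improvement is defined in the same way.

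**Population.** SAP 7 states that "analyses of secondary efficacy variables will be performed using the ITT population only". The table in SAP 7.2 lists SNOT-22 and ACQ improvement with ITT as population and NRI as imputation, at Weeks 4, 8 and 10. SAP 4.7 defines the set: "The Intent-To-Treat (ITT) Population will consist of all treated subjects with at least one post-baseline assessment of SNOT-22". Protocol 11.2.2 has the same definition.

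**Timing.** In Protocol 8.1.2, "There will be a telephone encounter one week into this Treatment Period", and no questionnaire is scheduled with that call. The first scheduled post-baseline SNOT-22 is at the next visit: "After four weeks of treatment, subjects will return to the site for Week 4 Treatment Visit".

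**Discontinuation.** Protocol 8.1 says: "If a subject is prematurely discontinued from treatment, all assessments planned at the End of Treatment visit should be performed". Those assessments include the SNOT-22.

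**The concern.** NRI needs no post-baseline data. A treated subject with no later score is a non-responder by the rule itself. Restricting the analysis to a set whose entry condition is a post-baseline SNOT-22 removes such subjects before the rule can act, so they are left out rather than counted as failures.

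An arm's response rate rises when such subjects are dropped, and the comparison shifts if the arms lose different numbers. The SAP has no other responder analysis that would show this: multiple imputation is planned for the primary variable only, and nothing is run on all treated or all randomized subjects. For ACQ-7, entry to the denominator also depends on a different questionnaire.

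**Working it through.** **The plan's own figure.** The only figure nearby is the 90% power of SAP 4.5, for the primary analysis. With 38 per arm, difference 12 and SD 16, the noncentrality is 12 / (16 × √(2/38)) = 3.27. That gives power of 90.5% (normal) or 89.7% (t), so the figure reproduces. It is not in question here. The plan states no response or dropout rate.

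**Who is affected.** Reading the sections together:

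| Treated subject | In ITT? | Handling in the Week 8 responder analysis |
|---|---|---|
| Week 4 SNOT-22 present, Week 8 missing | Yes | Failure, by NRI |
| Stops before Week 4, gives a SNOT-22 at discontinuation | Yes | In the denominator; the visit that score belongs to is not stated |
| Stops before Week 4, gives no later SNOT-22 | No | Not counted at all |

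The gap is the third row only.

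**Effect on one arm.** Let m be the responders among 38 treated and k the early losses with no later score, all non-responders under NRI.

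- All treated: m/38. ITT: m/(38 − k). The ratio is 38/(38 − k).
- k = 2: 38/36 = 1.056. k = 4: 38/34 = 1.118.
- Example with m = 20: 20/38 = 52.6%, 20/36 = 55.6%, 20/34 = 58.8%.

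**Effect on the comparison.** Assume 23 responders on ifetroban and 15 on placebo, of 38 treated each. The test is that of SAP Appendix A, Z = (r1 − rp)/s with s² = r1(1 − r1)/n1 + rp(1 − rp)/np. On all treated subjects r1 = 0.605, rp = 0.395 and s = 0.112, so Z = 0.2105/0.1121 = 1.88.

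| Losses (ifetroban/placebo) | Rates | Difference (points) | Two-sided p |
|---|---|---|---|
| All treated, NRI | 60.5% vs 39.5% | 21.1 | 0.060 |
| ITT, 2/2 | 63.9% vs 41.7% | 22.2 | 0.053 |
| ITT, 4/4 | 67.6% vs 44.1% | 23.5 | 0.044 |
| ITT, 2/0 | 63.9% vs 39.5% | 24.4 | 0.030 |
| ITT, 4/0 | 67.6% vs 39.5% | 28.2 | 0.013 |
| ITT, 0/4 | 60.5% vs 44.1% | 16.4 | 0.159 |

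Two-sided values are shown for comparability. Appendix A as written gives the one-sided p-value, which is a separate matter.

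**Effect on the error rate.** Assume true response of 50% in both arms among all treated subjects, and enumerate the two binomials exactly under the same Z rule. The ITT rates are then 50% × 38/36 = 52.8% (k = 2) or 50% × 38/34 = 55.9% (k = 4) on ifetroban, against 50% on placebo.

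| Losses (ifetroban/placebo) | Two-sided 0.05 | One-sided 0.05, favoring ifetroban |
|---|---|---|
| 0/0 | 5.1% | 5.1% |
| 2/0 | 5.8% | 9.2% |
| 4/0 | 8.9% | 14.2% |

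For true response between 40% and 60%, the 4/0 case gives 7.2% to 10.4% two-sided and 11.0% to 16.8% one-sided.

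**The case against.** A reader might infer that the ITT definition defeats NRI altogether. It does not. NRI still acts on every ITT subject who misses a given visit, and SAP 5.1 bars rescuing such a subject with a carried-forward score. For ACQ-7, a subject with a SNOT-22 but no ACQ-7 stays in the set and counts as a failure.

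A reader might also infer that all early dropouts vanish. Protocol 8.1 asks for the End of Treatment assessments at premature discontinuation, and Protocol 9.1 asks for every effort to complete the final assessments. A subject who stops early and attends stays in ITT. Those left out are mainly subjects who are lost to follow-up or who withdraw consent to all further activity, and they may be few.

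A third tempting inference is that the plan favors ifetroban through early tolerability losses. The documents do not support it. Protocol 5.1 reports no treatment-related adverse events on ifetroban before the aspirin challenge in the earlier small study, and Protocol 5.4 calls the dose well tolerated. That does not exclude unequal loss, but nothing indicates which arm would lose more. Losses mainly on placebo work against ifetroban, as the 0/4 row shows.

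Finally, SAP 6.1 will report the reasons for exclusion from ITT by arm, so a reader of the results could rebuild the treated denominator.

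All of this stands and limits the size of the problem. It does not remove the mismatch: the rule is written without a post-baseline condition, and the population imposes one.

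**Conclusion.** The point holds in limited form and is minor. NRI as planned does not reach treated subjects with no post-baseline SNOT-22, and no planned responder analysis includes them. Each such loss raises that arm's rate by the factor 38/(38 − k), about 6% in relative terms for two losses and 12% for four. Equal losses move the difference little (21.1 to 22.2 points at 2/2), although 4/4 takes the example from p = 0.060 to 0.044. Unequal losses move it more, in either direction.

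These sizes rest on assumed responder counts, assumed early losses and 38 treated per arm. They are illustrations, not forecasts or bounds. The primary result does not turn on this point: it is an ANCOVA with LOCF, in which NRI plays no part. The protocol synopsis describes the responder analyses as ancillary.

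**What to change.** In SAP 7.2:

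1. Run the SNOT-22 and ACQ-7 responder analyses with NRI on all randomized and treated subjects, which is the Safety Population already defined in SAP 4.7. Count those with no post-baseline score as non-responders. State in Appendix A that n1 and np are the treated counts.
2. Keep the analysis on the current ITT set as a sensitivity analysis.
3. State which visit a SNOT-22 taken at discontinuation is assigned to, since this decides whether the subject has a Week 4 or Week 8 value or is missing there.

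The cost is a short SAP edit and slightly lower response rates. No new data are needed, and SAP 1 allows revision before any unblinded analysis. Subjects randomized but never treated would still be outside the analysis.
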